## 7. Analysis Subsets

### 7.1 Full Analysis Set

The full analysis set will consist of all enrolled subjects. Analyses for demographics and baseline characteristics will use this analysis set.

### 7.2 Safety Analysis Set

The safety analysis set will consist of all subjects who receive at least 1 dose of romiplostim. The analyses of all safety endpoints will be based on the safety analysis sets.

### 7.3 Efficacy Analysis Set

The efficacy analysis set will consist of all subjects who receive at least 1 dose of romiplostim. The analyses of all efficacy endpoints will be based on the efficacy analysis sets.

### 7.4 Per Protocol Analysis Set

The per protocol analysis set will consist of all subjects who receive at least 1 dose of romiplostim and met all eligibility criteria. Sensitivity analysis using the per protocol analysis set may be explored for the primary efficacy endpoint.

## 8. Interim Analysis and Early Stopping Guidelines

Interim analyses will be conducted to support regulatory filings and accumulating data for this study will be summarized to provide ongoing assessments of the safety of

---

romiplostim. These interim analyses will occur at least annually until the end of the study.

## **9. Data Screening and Acceptance**

### **9.1 General Principles**

The objective of the data screening is to assess the quantity, quality, and statistical characteristics of the data relative to the requirements of the planned analyses.

### **9.2 Data Handling and Electronic Transfer of Data**

All data for this study will be received from Amgen's data management department.

### **9.3 Handling of Missing and Incomplete Data**

Missing and incomplete data will be identified through a review of the tables and listings. Attempts will be made to characterize the missing data. In general, data will be analyzed as retrieved from the clinical database except for analyses requiring imputations of missing (or incomplete) dates of adverse events and concomitant ITP medications, and missing platelet counts. The imputed dates will be written to the Case Report Tabulation (CRT) data but not to the raw data retrieved from the clinical database. The imputation algorithm will be described in the Data Definition Table (DDT).

### **9.4 Outliers**

No statistical test for outliers will be performed. Any outliers identified will be investigated by the study team and will be included in the database unless determined to be an error or there is supporting evidence or explanation to justify exclusion. Any outliers excluded from the analysis will be discussed in the Clinical Study Report (CSR), including the reasons for exclusion and the impact of their exclusion on the study.

### **9.5 Validation of Statistical Analyses**

Programs will be developed and maintained, and output will be verified according to processes described in procedures or technical manuals about the "Configuration Management of Statistical Analysis and Reporting Systems", "Statistical Analysis and Reporting System Development and Validation", and "Development of Statistical Analysis and Reporting Systems".

Tables, figures and listings will be produced with validated standard macro programs where standard macros can produce the specified outputs.

The production environment consists of Amgen-supported versions of the SAS System running on the Sun Solaris operating system. Because it is common for multiple versions of SAS to be available during the study period, the SAS version used to

---

produce analyses will be documented in the validation documentation and the clinical study report. Allow for use of S-plus as option for exploratory analysis.

## **10. Statistical Methods of Analysis**

### **10.1 General Principles**

Summary statistics will be provided for the primary and secondary endpoints.

### **10.2 Subject Accountability**

The number of subjects who enrolled into the study, received at least 1 dose of investigational product, completed the Investigational Product, completed the study and prematurely withdrew, and the reason for premature withdrawal, will be summarized for all subjects and by age groups (<6, 6-<12, 12-<18 years). The number of subjects who enrolled into the study will be tabulated by center.

### **10.3 Important Protocol Deviations**

Important Protocol Deviations (IPDs) categories are defined by the study team before the first patient visit and updated during the IPD reviews throughout the study prior to database lock. If a snapshot is being taken during the study rather than a database lock at the end of the study, categories should be updated during the IPD reviews throughout the study prior to database lock. These definitions of IPD categories, sub-category codes and descriptions will be used during the course of the study. The final IPD list is used to produce the Summary of IPDs table and the List of Subjects with IPDs. The IPDs will be summarized by categories.

### **10.4 Demographic and Baseline Characteristics**

Summaries of demographics and baseline characteristics will be provided based on the Full Analysis Set. The following demographic and baseline characteristics will be summarized for the full analysis set using descriptive statistics: age, age groups, race, sex, height, weight, platelet counts, baseline hematology, baseline physical examination, baseline vital signs, and medical history.

### **10.5 Efficacy Analyses**

The efficacy analysis will be based on the Efficacy Analysis Set, which includes all subjects who receive at least one dose of romiplostim.

Summary statistics of platelet counts and responses will be provided weekly at Week 1 to 8 and then every 4 weeks for all subjects in the efficacy analysis set and by age groups (<6, 6-<12, 12-<18 years). Platelet response is defined as platelet count

---

$\geq 50 \times 10^9/L$ . Platelet counts within 4 weeks after rescue medication use will not be deemed as platelet responses.

The percentage of time with platelet response starting from Week 2 in the first 6 months of the treatment period will be estimated for all treated subjects and by age groups (<6, 6-<12, 12-<18).

The percentage of time with platelet response from Week 2 till the end of the treatment period will be estimated for all treated subjects and by age groups (<6, 6-<12, 12-<18).

The percentage of time with an increase in platelet counts  $\geq 20 \times 10^9/L$  above baseline starting without rescue medication use during past 4 weeks from Week 2 until the end of the treatment period will be estimated for all treated subjects and by age groups (<6, 6 <12, 12-<18).

The proportion of subjects who used rescue medication for ITP during the study will be summarized by preferred terms. Rescue medication is defined as any medication or transfusion, other than romiplostim and excluded medications, that is administered after enrollment to the subject during screening or throughout the treatment period with the intent of raising platelet counts or prevent bleeding and includes concomitant medications for ITP where the dose and/or schedule is increased.

The proportion of subjects who achieved sustained platelet response for 24 weeks or longer will be summarized. A sustained platelet response is defined as a platelet count  $\geq 50 \times 10^9/L$  without the use of any ITP medications.

The proportion of subjects who had a splenectomy during the study will be summarized for the subjects who entered this study without splenectomy.

Number and percentage of subjects who started self-administration of romiplostim during the study will be summarized.

## **10.6 Safety Analyses**

The safety analysis will be based on the Safety Analysis Set, which includes all subjects who receive at least one dose of romiplostim administration.

### **10.6.1 Adverse Events**

The safety endpoint for this study is the exposure adjusted rates of adverse events. The exposure adjusted incidence rates as well as subject incidence rates of adverse events will be summarized by system organ class and by preferred term according to the MedDRA dictionary. Exposure adjusted rate is defined as total number of events divided

---

by time of duration when subjects were under observation. The summary includes all treatment-emergent adverse events recorded from the start of investigational product on this study, or any worsening of conditions present at baseline before dosing in this study. This summary for adverse events will be performed for the following categories

- All adverse events
- Romiplostim related adverse events/serious adverse events
- Serious adverse events
- Grade 3 or above adverse events
- Adverse events leading to withdrawal from the study
- Adverse events of interest (hemorrhage events, etc.)

In addition, incidence and exposure adjusted rates of adverse events by period may also be explored. The overall summary of exposure adjusted incidence rates as well as subject incidence rates of adverse events by age groups (<6, 6-<12, 12-<18 years), race, sex will also be provided.

Subject listings for all adverse events, serious adverse events, and adverse events leading to withdrawal from the study will be provided.

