Bleeding was the only event of interest observed on study. When adjusted for exposure duration, the rate of bleeding was 7.3 events per 100 subjects-weeks in the romiplostim arm and 11.9 events per 100 subject-weeks in the placebo arm. Bleeding events were mostly mild and occurred early in the treatment period when platelet counts were $< 50 \times 10^9/L$. No bleeding adverse events were considered to be serious or treatment related.

Product: Romiplostim
Protocol Number: 20101221
Date: 15 August 2014

Page 18 of 69

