3.1.1 Subjects With an Onset of Sustained Platelet Response

During the treatment period, romiplostim doses will be adjusted as outlined in [Table 1](#). Subjects who dose reduce romiplostim such that they no longer require treatment with romiplostim, no longer require ITP medications (concomitant or rescue), and have an onset of a sustained platelet response (defined as a consecutive platelet counts $\geq 50 \times 10^9/L$) will be monitored for at least 6 months beginning with the first platelet count $\geq 50 \times 10^9/L$. Subjects whose platelet count remains $\geq 50 \times 10^9/L$ in the absence of any medications for ITP for at least 6 months will then be followed every 12 weeks for the duration of the 36-month treatment period.

If during the 36-month treatment period the platelet count subsequently falls below $< 50 \times 10^9/L$, treatment with romiplostim at the initial starting dose may be resumed. Subsequent doses will be adjusted as shown in [Table 1](#). Clinic visits will be resumed per the Schedule of Assessments ([Table 2](#)).

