9.2 Reporting of Adverse Events

9.2.1 Reporting Procedures for Adverse Events That do not Meet Serious Criteria

The investigator is responsible for ensuring that all adverse events observed by the investigator or reported by the subject that occur after first dose of investigational product through the end of treatment period are reported using the applicable eCRF (eg, Adverse Event Summary CRF).

Because all subjects who enter the study will be diagnosed with ITP according to the ASH guidelines, ITP should not be reported as an adverse event during the conduct of the study.

The investigator must assign the following adverse event attributes:

- adverse event diagnosis or syndrome(s), if known (if not known, signs or symptoms)
- dates of onset and resolution (if resolved)

- severity
- assessment of relatedness to romiplostim
- action taken

The adverse event severity grading scale used will be the Common Terminology Criteria for Adverse Events (CTCAE) version 3.0 grading scale. The severity grading scale used in this study is described in [Appendix A](#).

The investigator must assess whether the adverse event is possibly related to the romiplostim. This relationship is indicated by a “yes” or “no” response to the question: Is there a reasonable possibility that the event may have been caused by the romiplostim?

The investigator must assess whether the adverse event is possibly related to any study-mandated activity (eg, administration of investigational product, protocol-required therapies, device(s) and/or procedure (including any screening procedure(s))). This relationship is indicated by a “yes” or “no” response to the question: “Is there a reasonable possibility that the event may have been caused by a study activity (eg, administration of investigational product, protocol-required therapies, device(s)), and/or procedure?”

The investigator is responsible for reviewing laboratory test results and determining whether an abnormal value in an individual study subject represents a clinically significant change from the subject’s baseline values. In general, abnormal laboratory findings without clinical significance (based on the investigator’s judgment) are not to be recorded as adverse events. However, laboratory value changes that require treatment or adjustment in current therapy are considered adverse events. Where applicable, clinical sequelae (not the laboratory abnormality) are to be recorded as the adverse event.

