10.3.2.2 Safety Endpoints

The exposure-adjusted incidence rates as well as subject incidence rates of adverse events will be summarized by system organ class and by preferred term according to the MedDRA dictionary. Exposure-adjusted rate is defined as total number of events divided by time of duration when subjects were under observation. The summary includes all treatment-emergent adverse events recorded from the start of IP on this study, or any worsening of conditions present at baseline before dosing in this study. This summary for adverse events will be performed for the following categories

- all adverse events
- romiplostim-related adverse events
- serious adverse events
- adverse events leading to withdrawal from the study
- adverse events of interest (hemorrhage events, etc.)

In addition, incidence and exposure-adjusted rates of adverse events by period may also be explored.

Subject listings for all adverse events, serious adverse events, and adverse events leading to withdrawal from the study will be provided.

The incidence and percentage of subjects who develop anti-romiplostim antibodies (binding and if positive, neutralizing) at any time will be tabulated.

Summary statistics will be provided for blood chemistry and CBC at each time point. Shift tables between the worst post-baseline and baseline values will be provided (based on the National Cancer Institute CTCAE, version 3.0).

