## 3. Study Overview

### 3.1 Study Design

This is a phase 3b single arm, open-label, multicenter study evaluating the percentage of time pediatric subjects with ITP have a response while receiving romiplostim, defined as a platelet count  $\geq 50 \times 10^9/L$  and in the absence of ITP rescue medications in the past 4 weeks. This protocol will provide open-label romiplostim to thrombocytopenic pediatric subjects with ITP diagnosed for at least 6 months and who have received at least 1 prior ITP therapy (excluding romiplostim) or are ineligible for other ITP therapies.

---

The study design consists of a 4-week screening period, up to a 3-year treatment period, an end of treatment (EOT) visit and an end of study (EOS) visit.

Approximately 200 children with ITP will be enrolled into the study and receive weekly romiplostim until they complete the study, discontinue participation in the study for any reason, or the study ends.

The overall study design is described by a study schema at the end of the protocol synopsis section (refer to the study protocol).

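### The exposure-adjusted adverse-event rate is divided by observation time, so drug-free remission can dilute the on-drug rate of romiplostim-related events

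*SAP*

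**What the plan says.** SAP 10.6.1 names its main safety measure: "The safety endpoint for this study is the exposure adjusted rates of adverse events". Protocol 10.3.2.2 defines it: "Exposure-adjusted rate is defined as total number of events divided by time of duration when subjects were under observation". SAP 10.6.1 uses the same denominator, dividing "by time of duration when subjects were under observation". Neither document defines when a child is under observation, and neither limits the denominator to time on romiplostim.

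The numerator is "treatment-emergent adverse events recorded from the start of investigational product on this study", with no stop tied to the last dose. Under Protocol 9.2.1, adverse events "that occur after first dose of investigational product through the end of treatment period are reported".

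Protocol 3.1.1 covers children who no longer need romiplostim or any other ITP medication. They are monitored for at least 6 months, and those whose counts hold "will then be followed every 12 weeks for the duration of the 36-month treatment period". Protocol 7.6 and 7.7 agree: for those who complete 36 months and have been off all ITP treatment for at least 4 weeks, the end-of-treatment visit comes after month 36.

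For serious events, Protocol 9.2.2 closes the required reporting window 30 days after the last dose in children with sustained response who never restart.

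SAP 4.3 plans duration-adjusted rates overall and for each 6-month period. SAP 10.6.1 makes by-period rates optional. Neither splits time into on drug and off drug.

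**The concern.** A rate called exposure adjusted will be read as events per unit of time on drug. As defined, it pools time on drug with what may be years without drug. Events judged related to romiplostim should be few long after the last dose, so that pooled time adds to the denominator and little to the numerator. The named safety measure of a long-term paediatric study would then lean in the favourable direction. If the off-drug share grows over the study, related-event rates in later 6-month periods would fall through dilution alone, which could be taken for improving tolerability.

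Serious events have a second problem. In a child who stays in remission without restarting, person-time runs on after the required reporting window has closed. Even read as a rate per observation time, the serious-event rate then includes time with no required event capture.

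**Working it through.** The documents give no adverse-event rate, remission rate or off-drug person-time for this study, so there is no planned figure to reproduce. The check is person-time algebra under stated assumptions.

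**Inputs from the documents.** Follow-up T = 36 months (SAP 3.1: "up to a 3-year treatment period"). Denominator: time under observation (SAP 10.6.1, Protocol 10.3.2.2). Drug-free follow-up to month 36 (Protocol 3.1.1). Serious-event window of 30 days after the last dose for children in remission who never restart (Protocol 9.2.2).

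**Assumptions.** f = share of children who go off drug; m = months off drug for each of them; k = off-drug event rate divided by on-drug event rate. All children are followed for 36 months.

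**Formula.** Off-drug share of person-time s = f × m / 36. Reported rate / on-drug rate = (1 − s) + s × k.

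| f | m | s | k = 0 | k = 0.5 | k = 1 | k = 1.5 |
|---|---|---|---|---|---|---|
| 5% | 12 | 1.7% | 0.983 | 0.992 | 1.000 | 1.008 |
| 10% | 24 | 6.7% | 0.933 | 0.967 | 1.000 | 1.033 |
| 20% | 24 | 13.3% | 0.867 | 0.933 | 1.000 | 1.067 |
| 30% | 30 | 25.0% | 0.750 | 0.875 | 1.000 | 1.125 |

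**Related events.** With none off drug (k = 0), the rate is understated by 1.7% to 25%. For one child with 12 months on drug and 24 off, the ratio is 12/36 = 0.33.

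**Bleeding.** Bleeds in remission are also counted, so the result depends on k. At k = 0.5 the understatement is 0.8% to 12.5%. At k = 1 there is none. At k = 1.5 the on-drug rate is overstated by 0.8% to 12.5%.

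**Early leavers.** Non-responders (Protocol 6.2.3) and children who have a splenectomy (Protocol 6.7) leave before month 36, which raises the off-drug share. Illustration with assumed values: f = 20%, m = 18, all others averaging 24 months. Off-drug time is 0.2 × 18 = 3.6 months per child and total time is 0.2 × 36 + 0.8 × 24 = 26.4 months, so s = 3.6/26.4 = 13.6%. With everyone followed for 36 months it would be 3.6/36 = 10%.

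**By period.** If a share p of person-time in a 6-month period is off drug, the ratio for that period is (1 − p) + p × k. The dilution grows with time only if p grows.

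**Serious events.** The share of a child's off-drug time that lies outside the required window is 1 − 30/(365.25 × years off): 92% for 1 year, 96% for 2 years, 97% for 2.5 years. This needs no assumption about k.

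**Does SAP section 6 solve it?** Its treatment duration runs from first dose to last dose plus 7 days. That would remove remission lasting to the end of study, but would keep drug-free gaps in children who restart. SAP 10.6.1 does not refer to it.

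**The case against.** Events per unit of observed time is a legitimate rate, and the plan states its definition openly. Subject incidence is reported alongside and does not depend on this denominator. Listings of all adverse events and of dosing are planned. All of this stands, so the fault lies in the label and in reading the figure as an on-treatment rate.

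Because being under observation is not defined, the SAP section 6 treatment duration might be what was meant. Most of the dilution would then disappear. This cannot be ruled out, and it is a reason to write the denominator down.

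The size depends wholly on assumptions. At low remission rates it is 1% to 3%.

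Three stronger readings are tempting and not supported:

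- *Bleeding is understated.* Non-serious bleeds in remission enter the numerator, so this holds only if bleeding is rarer off drug. That is plausible: sustained response requires counts of at least 50 × 10⁹/L, and Protocol 2.4 places phase 2 bleeds mostly early, at lower counts. No off-drug bleeding rate is given.
- *The rate cannot be compared with the phase 2 figure.* Protocol 2.4 says: "When adjusted for exposure duration, the rate of bleeding was 7.3 events per 100 subjects-weeks in the romiplostim arm". It does not define that denominator, and no comparison is planned.
- *Any fall over time is an artefact.* Bleeding was early in phase 2, so a real decline on drug could also occur.

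On serious events, the schedule of assessments (Protocol Table 2) lists them at every visit type, and 9.2.2 asks for later events to be reported if the investigator learns of them. Some capture may therefore continue. Section 9.2.2 nevertheless removes the duty to monitor actively, and sends late reports to the safety database for expedited reporting.

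An on-drug window of only 7 days would have its own bias. Protocol 6.2.2 recognises that counts can drop quickly when a dose is withheld, and a resulting bleed could fall outside so short a window.

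**Conclusion.** The concern holds in limited form. The label and the denominator disagree, and on a plain reading drug-free remission to month 36 counts as exposure. The related-event rate can understate on-drug risk by about 2% to 25%, if 5% to 30% of children are off drug for 12 to 30 of 36 months and have no related events then. Bleeding is understated by about 1% to 12.5% if its off-drug rate is half the on-drug rate, and not at all if the rates are equal. These are ranges under assumptions, not estimates for this trial. The serious-event mismatch follows from the reporting rule in Protocol 9.2.2 and does not depend on those assumptions about event rates, although its effect on the rate depends on how many children stay in remission and what is captured after the window closes. The change is worth making because it affects the named safety measure and is cheap.

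**What to change.** In SAP 10.6.1:

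1. Add an on-drug rate, with events and person-time both counted over dosing periods plus one pre-specified post-dose window. The 30 days already used in Protocol 9.2.2 would serve, with last dose plus one week (SAP section 6) as a sensitivity analysis. Briefly withheld doses stay inside the window. Drug-free remission beyond it, including gaps before a restart, is excluded.
2. Keep the present rate beside it, labelled as per observation time, and define when observation starts and ends.
3. Show drug-free events and person-time separately, overall and by 6-month period, and settle whether by-period rates are planned (SAP 4.3) or optional (SAP 10.6.1).
4. Limit person-time for serious-event rates to the serious-event reporting window. The sponsor should reconcile Protocol 9.2.2 with Table 2 on when that window ends.

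The cost is SAP text and some programming from dosing dates already collected. The reported on-drug rate may be slightly less favourable. No treatment or visit rule changes.

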8.2.1 Reasons for Removal From Treatment

Reasons for removal from romiplostim or observation might include the following:

- **protocol specified criteria**
- subject request (or the subject's legally authorized representative)
- safety concern (eg, due to an adverse event, ineligibility determined, protocol deviation, non-compliance, requirement for alternative therapy, pregnancy)
- death
- lost to follow-up
- decision by Sponsor (other than subject request, safety concern, lost to follow-up)

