8.2.2 Reasons for Removal From Study

Reasons for removal of a subject from the study are as follows:

- **protocol specified criteria**
- decision by sponsor
- withdrawal of consent from study
- death
- lost to follow-up

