9. SAFETY DATA COLLECTION, RECORDING, AND REPORTING

9.1 Adverse Events

9.1.1 Definition of Adverse Events

An adverse event is defined as any untoward medical occurrence in a clinical trial subject. The event does not necessarily have a causal relationship with study treatment. The investigator is responsible for ensuring that any adverse events observed by the investigator or reported by the subject are recorded in the subject's medical record.

The definition of adverse events includes worsening of a pre-existing medical condition. Worsening indicates the pre-existing medical condition (eg, diabetes, migraine headaches, gout) has increased in severity, frequency, and/or duration, and/or has an association with a significantly worse outcome. A pre-existing condition that has not worsened during the study, and involves an intervention such as elective cosmetic surgery or a medical procedure while on study is not considered an adverse event.

The investigator's clinical judgment is used to determine whether a subject is to be removed from treatment due to an adverse event. In the event a subject, or subject's

Product: Romiplostim
Protocol Number: 20101221
Date: 15 August 2014

Page 42 of 69

legally acceptable representative requests to withdraw from protocol-required therapies or the study due to an adverse event, refer to [Section 8.1](#) for additional instructions on the procedures recommended for safe withdrawal from protocol-required therapies or the study.

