- The summary for adverse events will be performed for the categories of all adverse events, romiplostim-related adverse events, serious adverse events, adverse events leading to withdrawal from the study, adverse events of interest (hemorrhage events, etc.). Both subject incidence and duration-adjusted rates of adverse events are calculated for overall study duration and by study period at every 6 months. Subject listings for all adverse events, serious adverse events, adverse events leading to study withdrawal, and fatal adverse events are provided.

- Summary statistics are calculated for blood chemistry and CBC at each visit. Shift tables between the worst post-baseline and baseline values are provided based on the National Cancer Institute CTCAE, version 3.0.

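### The only adverse-event discontinuation category is withdrawal from the study, so events that end romiplostim without being recorded as the reason for leaving the study go uncounted as such

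*SAP*

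**What the plan says.** Three places define the adverse-event summaries. Protocol 10.3.2.2 lists five categories, one of them "adverse events leading to withdrawal from the study". SAP 4.3 repeats those five. SAP 10.6.1 adds grade 3 or above, which makes six, and keeps "Adverse events leading to withdrawal from the study". The listings follow the same scheme: "Subject listings for all adverse events, serious adverse events, and adverse events leading to withdrawal from the study will be provided". SAP 4.3 also lists fatal events. No section plans a table or an adverse-event listing of events that led to stopping romiplostim.

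The protocol's disposition rules distinguish treatment from study. Section 8.2.1, on removal from treatment, includes "safety concern (eg, due to an adverse event, ineligibility determined, protocol deviation, non-compliance, requirement for alternative therapy, pregnancy"). Section 8.2.2 opens with "Reasons for removal of a subject from the study are as follows" and names protocol criteria, sponsor decision, consent withdrawal, death and loss to follow-up. Section 9.1.1 says "The investigator's clinical judgment is used to determine whether a subject is to be removed from treatment due to an adverse event".

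**The concern.** The planned category is tied to one kind of disposition (leaving the study), while the protocol describes an adverse-event stop chiefly as another kind (coming off the drug). A child can do the second without the first. That child's event is then not identified in any summary as having ended treatment.

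Long-term safety is a stated secondary objective, treatment lasts up to 3 years, and there is no control arm. In that setting, how often adverse events make children stop the drug is one of the main tolerability figures. A reader of the report would naturally take the study-withdrawal line as that figure. It may be lower, and nothing planned shows the gap by system organ class and preferred term.

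**Working it through.** No stated figure is in dispute, so the check is a comparison of sections.

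1. **What is counted.** Protocol 10.3.2.2, SAP 4.3 and SAP 10.6.1 all count events leading to study withdrawal. The SAP follows the protocol's wording, so this is a gap shared by both documents and not a departure of the SAP from the protocol.

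2. **Where an adverse-event stop is placed.** Section 8.2.1 puts it among the reasons for removal from treatment. Section 9.1.1 frames the investigator's decision the same way. Section 8.2.2 contains no adverse-event or safety reason.

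3. **Whether the two dispositions can separate.** They can. Section 8.1 allows a subject to decline further drug and continue in the study. Section 7.1.3 takes children with neutralizing antibodies off treatment and asks them back every 3 months until the antibodies are undetectable or at least 1 year has passed. Section 12.4 extends data collection to subjects no longer on protocol therapy.

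4. **Whether they can coincide.** They can. Section 9.1.1 also covers a request to leave the study because of an adverse event. Section 9.2.2 covers permanent withdrawal from the study for a serious one. Section 7.1.4 of the supplement for the EU, Switzerland and Turkey describes children stopped for collagen as withdrawn from the study.

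5. **Effect on the reported figure.** Let K be the number of children who stop romiplostim for an adverse event, and s the share of them whose event is also recorded as the reason for study withdrawal. The planned category then shows K × s children. Assuming one stopping event per child, the exposure-adjusted rate (events divided by time under observation) shrinks by the same factor s, because only the numerator changes.

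6. **Illustration.** The documents give neither K nor s. Taking 200 children and assumed stopping rates of 2%, 5% and 10%:

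| Assumed rate | K = 200 × rate | Shown if s = 1 | Shown if s = 0.5 | Shown if s = 0 |
|---|---|---|---|---|
| 2% | 4 | 4 | 2 | 0 |
| 5% | 10 | 10 | 5 | 0 |
| 10% | 20 | 20 | 10 | 0 |

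The column s = 0 follows only from reading 8.2.2 literally and on its own. Step 4 argues against it. The table shows how far the result depends on coding and is not an estimate.

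7. **Whether the data exist.** They do. Section 9.2.1 requires the action taken to be assigned for each adverse event, and protocol 10.3.4.3 and SAP 10.6.5 list the reason for ending the drug.

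**The case against.** The best case for the plan is that stopping the drug and leaving the study often coincide here. A child who stops while on drug has the EOT visit 1 week and the EOS visit 4 weeks after the last dose (7.7, 7.8). Those visits are also what 8.1 asks of early withdrawals and 6.2.3 of non-responders, so completing them does not show that a child was not withdrawn. The lead-in to 8.2.1 covers removal from observation as well as from the drug, so its adverse-event reason is not purely a treatment reason. This stands, and it narrows the group that is missed.

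A reader might infer from 8.2.2 that only deaths could enter the planned category, or that it will read close to zero. The documents do not support that. Sections 9.1.1 and 9.2.2 and supplement 7.1.4 foresee study withdrawal for an adverse event, a serious adverse event or collagen. Consent withdrawal, sponsor decision and protocol criteria can each have an adverse event behind them.

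A reader might also infer that these events vanish from the safety tables, or that a drug-administration listing is their only trace. Neither is so. The events still appear under all adverse events and, where they qualify, under related, serious, and grade 3 or above. Subject accountability (protocol 10.3.4.1, SAP 10.2) counts completion of the drug and of the study, and reasons for premature withdrawal. It does not say whether those reasons refer to the drug or the study, however, and it carries no adverse-event terms. The listing of reasons for ending the drug gives no incidence and no rate.

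**Conclusion.** The point holds in a limited form. The plan has no summary or listing of adverse events that led to stopping romiplostim, and the study-withdrawal category cannot stand in for one. It misses two groups: children who stop for an adverse event and remain under follow-up, and children whose event is not coded as the reason for leaving the study. For them the event is tabulated, but its role in ending treatment is not.

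The consequence is possible understatement of one tolerability figure, its incidence and its exposure-adjusted rate. The size cannot be estimated from the documents: it depends on how many children stop for an adverse event and on how sites code disposition, and neither is given. The primary endpoint is not affected. The change is worth making because long-term safety is an objective of an uncontrolled study and the data needed are already collected.

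**What to change.** In protocol 10.3.2.2, SAP 4.3 and SAP 10.6.1, add a category for adverse events leading to permanent discontinuation of romiplostim. Give it the same subject incidence, exposure-adjusted rate and listing as the other categories.

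Derive it from the action-taken field of each adverse event. The contingency form in Appendix A separates permanent discontinuation from a withheld dose; confirm that the routine eCRF makes the same distinction. Cross-check the result against the recorded reason for ending the drug and resolve mismatches before database lock. Keep the study-withdrawal category beside it, so that both dispositions can be read.

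The cost is one extra table, one extra listing and the matching wording. No new data are collected, and neither visits nor treatment rules change.
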